3.3 Outcome measures/endpoints

Outcome measures were determined after discussions with PPIE collaborators and a search of the COMET Initiative database (terms "Neurology", "Acute Stroke", "Published") for acute stroke trial core outcome sets. Two published recommendations were identified [29, 30] which incorporate survival, stroke recurrence, patient reported outcome measures (PROMs) across all domains including motor/non-motor problems, cognition, mood. However, whilst mRS is a standard outcome measure, there is no ubiquitous or agreed set of outcome/assessment scales used consistently in acute stroke trials. Outcome measures were chosen in partnership with the CLASP PPIE group and are aligned with the above recommendations to include survival, stroke recurrence and PROMs (quality of life and stroke-related health status). Caregiver burden was considered to be an important outcome measure by the PPIE group in view of the relatively poor prognosis of patients with PSP. The primary and secondary outcome measure scales (mRS [31], EQ-5D-5L [32], Home time [33], Stroke Impact Scale [34] and Zarit Caregiver Burden [35]) are well-established in stroke research and can be collected using telephone and postal assessments. The assessments will be centralised and undertaken by research staff blinded to treatment allocation. The timing of outcome assessments (described below) refers to time from randomisation.

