3.3.1 Primary outcome

Modified Rankin Scale (mRS) score (a measure of functional outcome) at 90 days (+/-14 days) assessed by virtual online assessment or telephone using centralised, blinded, trained raters.

Postal questionnaires can be used only in the event that online or telephone assessment is not possible to avoid loss to follow-up.

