3.3.2 Secondary outcomes

- All-cause mortality at 90 days
- Days spent in pre-admission usual place of residence at 90 days
- Cardiovascular mortality at 90 days
- Non-elective admissions by 90 days
- Stroke at 90 days
- Major cardiovascular events at 90 days
- EQ-5D-5L at 90 days
- Stroke Impact Scale at 90 days
- Zarit Caregiver Burden (ZBI-12) interview
- Clostridioides difficile infection within 90 days
- Ventricular arrhythmia within 7 days
- Health and social care resource use (index hospitalisation and post-discharge health and social care contact) up to 90 days to inform health economic analysis.

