7.6 Follow-up assessments

The trial will comprise of 4 visits: Screening, Randomisation, Day 7 and Day 90 follow-up.

The Day 7 (+3) visit will be carried out by research staff who will collect information such as the following from case notes:

- Information on safety outcomes including *C.difficile* infection, and occurrence of defined SAEs (see section 9)
- Clarithromycin dose, doses administered and route(s) of administration (including reasons for any non-administered doses)
- Other antibiotics and doses received
- Highest CRP concentration (mg/L) to Day 7 (+3) visit
- Highest WBC count and neutrophil count (x10⁹/l) to Day 7 (+3) visit
- Highest RR (/minute) to Day 7 (+3) visit
- Highest temperature (°C) recorded to Day 7 (+3) visit
- Highest NEWS-2 score to Day 7 (+3) visit
- Lowest oxygen saturations (%) to Day 7 (+3) visit
- Oxygen requirements
- Presence of unilateral or bilateral chest signs on examination
- Findings from clinical CXR or other chest radiology
- Contact details for follow-up (participant, consented caregiver, GP)

Participants and their caregivers/GP can be contacted by telephone, email or post between 1 week and 1 month prior to the due date of the Day 90 visit to confirm contact details and ongoing participation.

The Day 90 visit will involve local data collection by the research team and a centralised assessment (+/-7 for local research staff follow-up, +/-14 for central follow-up) by video or telephone.

Local research staff will collect the following data from the medical record at Day 90 (+/-7):

- Length of hospital stay (days)
- Mortality
- Discharge destination (remains in hospital, home, care home)
- Urgent or unplanned re-admissions
- Recurrent stroke or other vascular events

The centralised assessment will then be undertaken by appropriately trained University of Manchester staff blinded to treatment allocation. This will take place via video or telephone assessment after local research staff have carried out the mortality check. They will collect information such as the following measures:

- mRS
- Quality of Life (EQ-5D-5L)
- Stroke Impact Scale (SIS)
- Home time (number of days at usual place of residence [immediately prior to their admission] at day 90)
- Health and social care resource use (index hospitalisation and post-discharge health and social care contact up to 90 days)
- Caregiver quality of life (EQ-5D-5L)
- Zarit Caregiver Burden (ZBI-12)

The Day 90 visit marks the end of the study.

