Appendix 9 – Schedule of Procedures

| Procedure | Baseline | Day 7 (+3) | Day 90 (+/-7 for local follow-up) | Day 90 (+/-14 for central follow-up) |
|---|--------------|---------------|--------------------------------------|---|
| Screening | \checkmark | | | |
| Review eligibility | \checkmark | | | |
| Informed consent | \checkmark | | | |
| Data collection* | \checkmark | ~ | ✓ | ✓ |
| mRS | \checkmark | | | \checkmark |
| Vital signs assessment* (admission to randomisation) | ✓ | | | |
| Vital signs assessment* (randomisation to Day 5) | \checkmark | ✓ | | |
| Randomisation | \checkmark | | | |
| Start of antibiotic treatment | \checkmark | | | |
| Safety (SAEs) | | \checkmark | \checkmark | |
| Treatment compliance assessment | | ✓ | | |
| Follow-up* | | | \checkmark | \checkmark |

*See protocol sections 7.5 and 7.6 for full details

Draft version 0.6 – 10 December 2024

CLASP

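### The Day 90 contacts may be made from day 83, so secondary outcomes counted to 90 days can lose up to 7 days, and no stated step completes them

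*Protocol*

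**What the plan says.** Section 3.3 fixes the time origin: "The timing of outcome assessments (described below) refers to time from randomisation". Section 3.3.2 lists outcomes that build up over the whole period, for example "Non-elective admissions by 90 days", with stroke, major cardiovascular events, days in the usual residence, and health and social care resource use.

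Section 7.6 collects these in two ways:

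- **Local, from the record:** "Local research staff will collect the following data from the medical record at Day 90 (+/-7", covering length of stay, mortality, discharge destination, readmissions, and recurrent stroke or other vascular events. Appendix 9 repeats the window: "Day 90 (+/-7 for local follow-up".
- **Central, by interview:** the mRS, resource use to 90 days, and "Home time (number of days at usual place of residence [immediately prior to their admission] at day 90". Section 3.3.1 gives the mRS window: "at 90 days (+/-14 days) assessed by virtual online assessment or telephone".

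Section 7.6 also sets an order for the central call: "This will take place via video or telephone assessment after local research staff have carried out the mortality check". It then says that the Day 90 visit ends the study.

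Section 10.3.3 names logistic regression for readmission and for recurrent stroke or vascular events, general linear models for home time and resource use, and a Cox model for mortality.

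**The concern.** A symmetric window suits a status measured at one moment, such as the mRS. It does not suit a count up to a fixed day. A late contact does no harm, because events after day 90 can be dropped by date. An early contact cannot record what has not yet happened, and no analysis plan can restore it.

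A participant whose record is read on day 83 and who is readmitted on day 87 would enter the logistic model as having no readmission by 90 days. A participant called on day 83 cannot report more than 83 days at home. If early contacts are equally common in both arms, event counts, home time and costs are understated and absolute differences shrink somewhat. The within-trial economic analysis in section 10.10 also takes 90 days as its period.

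A smaller matter is that the nominal central window opens a week before the local window, although the local mortality check has to come first.

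**Working it through.** **Inputs.** Time runs from randomisation (3.3). The local window is 90 +/- 7 and the central window 90 +/- 14 (7.6, trial summary, Appendix 9). Mortality is one of the local items, and the central call follows the mortality check (7.6).

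**Windows in days**

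| Contact | Opens | Closes | Days in window | Days before day 90 |
|---|---|---|---|---|
| Local extraction | 90 - 7 = 83 | 90 + 7 = 97 | 15 | 7 |
| Central call, nominal | 90 - 14 = 76 | 90 + 14 = 104 | 29 | 14 |
| Central call, order rule kept | max(76, 83) = 83 | 104 | 22 | 7 |

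Central days 76 to 82 (7 days) fall before the local check can be in window. From day 83 to day 104 the windows and the order rule are compatible.

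**Shortfall.** For a contact on day d, the unobserved time is max(0, 90 - d).

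- Local, earliest: 90 - 83 = 7 days; 7/90 = 7.8%.
- Central, earliest with the order rule kept: also 7 days, 7.8%.
- Any contact on or after day 90: 0 days.

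**Is there a later step that fills the gap?** None of the candidates does so expressly:

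- Section 7.6 ends the study at the Day 90 visit, and 7.10 ends the trial at the last such visit.
- Section 9.2 sends hospitalisations linked to the stroke or to other conditions to the eCRF visit pages, not to continuous reporting.
- Section 7.7 makes registry linkage conditional on further funding and a separate protocol.
- Section 10.8 goes to the medical record for data that the telephone follow-up did not obtain. It does not cover a completed early call.
- Section 10.10 draws resource use partly from routine data, but sets no date for completing it.

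**Do the models absorb it?** A yes/no outcome in a logistic model and a day count or cost in a general linear model treat every participant as fully observed. Section 10.3.3 states no adjustment for a shorter period. Length of stay (negative binomial) is affected only in participants still in hospital at an early extraction.

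**From time to events.** The protocol gives no rates for these events, so 7.8% is a share of observation time. As an illustration, assume that events are spread evenly over 90 days and that a fraction f of records is read on day 83. The share of events missed is then f x 7.8%: 0 for f = 0, 3.9% for f = 0.5 and 7.8% for f = 1. Readmissions can occur only after discharge, so they may fall later than this assumption allows.

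**After the change.** With d >= 90 for both contacts, max(0, 90 - d) = 0, and every central day from 90 to 104 can follow a local check.

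**The case against.** Symmetric visit windows are common, and many contacts will fall on or after day 90 and lose nothing. Section 7.10 requires outcomes to be derived and queries resolved before database lock, so a diligent data manager might complete an early record. That is fair, but no passage requires it, and a day 83 extraction is complete as the protocol stands.

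Several stronger readings are tempting, and the documents do not support them:

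- **A loss of 14 days (14/90 = 15.6%) for home time and resource use.** This needs a call on day 76, before the local check is in window, and so breaks the order rule. The note to Table 2 in section 4 mentions a survival check, but for participants who have reached the 90-day period. It does not describe an earlier, separate check.
- **Lost deaths.** Section 9.10 requires all deaths in the eCRF without tying this to a visit date, and the Cox model can censor at last follow-up.
- **A truncated primary outcome.** The mRS is a status at interview. How to score someone interviewed alive who dies before day 90 is a derivation rule that may sit in the statistical analysis plan, which is not at hand.
- **Bias between arms.** Site staff know the allocation, but nothing suggests that they would time extractions by arm. Home time and resource use are collected by blinded central staff.
- **A serious contradiction between the windows.** Days 76 to 82 are unusable, and the remaining days work.

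**Conclusion.** The point holds for outcomes that accumulate to day 90: non-elective admissions, recurrent stroke, vascular events, length of stay, home time and resource use. Each can be cut short by up to 7 of 90 days (7.8%) in a participant contacted before day 90. That maximum assumes that the order rule in section 7.6 is kept and that the contact is made on the earliest permitted day. How often this will happen, and how many events it would miss, cannot be worked out from the protocol.

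The effect is confined to secondary, exploratory and economic outcomes. Mortality is less affected. The primary mRS and the sample size built on it are not. This is a cheap improvement that prevents an avoidable loss, and the two Day 90 windows should be reconciled at the same time.

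**What to change.** In section 7.6, the trial summary and Appendix 9:

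1. Do the local record extraction on or after day 90, for example day 90 to +7 or +14, and count only events dated on or before day 90. Closing at +7 (day 97) keeps at least 104 - 97 = 7 days for the central call after the latest check.
2. Open the central call at day 90 (day 90 to +14), so that home time and resource use are asked in the same single contact as the mRS and truncated at day 90. Section 3.3.1 would need the same window.
3. If the central call must stay open earlier, complete home time and resource use to day 90 from the later record extraction where possible, without a second call. The pre-call mortality check would then need its own stated timing, because the extraction would come later.

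The cost of items 1 and 2 is protocol wording and an eCRF date check, with no extra visit or call. The downside is that extraction and calls can no longer be done in the days before day 90. The usable central window falls from 22 days (83 to 104) to 15 (90 to 104). Item 3 adds a separate vital-status check at the site.

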7.7 Longer-term follow-up

Participants will be invited to consent to storage of their NHS number (or CHI in Scotland/H&C number in Northern Ireland) for longer-term follow-up using routinely-collected healthcare data (6-month mRS, recurrent stroke, recurrent PSP from the SSNAP registry/HES, longer-term survival (ONS) and dementia status). This will only be performed if additional funding is obtained, in which case a separate protocol will be developed for this activity.

7.8 Qualitative assessments

Study drug adherence will be assessed at Day 7 (+3) and reasons for non-adherence will be documented in the eCRF.

7.9 Withdrawal criteria

7.9.1 Withdrawal from clarithromycin treatment (intervention arm)

Participants may be withdrawn from the study treatment by local clinical teams in the event of a Serious Adverse Reaction (SAR) and it is felt that it is in the best interest of the patient to discontinue treatment. Participants allocated to the intervention arm will also be withdrawn from clarithromycin treatment in the event:

- Treatment is initiated with a prohibited medicine, where the prohibited medicine has not been temporarily discontinued by the local PI (see Appendix 2)
- Requirement for macrolide therapy as part of evolving antibiotic use
- Known toxin positive *C.difficile* infection
- The participant deteriorates after enrolment and becomes for palliative care only
- Onset of contraindications or major cautions to macrolide antibiotic use:
 - Hypersensitivity to clarithromycin, its excipients or other macrolide antibiotics
 - Diagnosis of long QT syndrome
 - Any event of QTc prolongation of >20ms compared to the baseline value
 - Ventricular tachycardia
 - Cardiac arrest
 - Any occurrence of severe hepatic impairment defined as AST, ALT or bilirubin >3 times ULN

Discontinuation of treatment by local clinical teams does not require withdrawal of the participant from the study and follow-up can be continued.

7.9.2 Withdrawal from study

Participants can decide to withdraw from the clinical trial and further follow-up at any time without giving any reason.

The CI, Co-CI or site Principal and Co-investigators have the right to withdraw patients from the study if deemed in the best interests of the participant or in the event of SARs, protocol violations, administrative or other reasons.

Full details of withdrawal should be recorded on the eCRF. Participants who withdraw from the study can consent to their vital status being checked and follow-up via medical records if they wish. A withdrawal form will be completed and retained in site files.

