Participants are free to withdraw consent for any aspect of the trial at any time and for any reason. They will be provided with contact details for local research staff via the PIS, which can be used should they wish to discontinue with the trial after discharge. If the participant wishes to withdraw from the study treatment, the reason(s) will be sought (but do not need to be given), and permission will be sought to continue with follow-up. If the participant wishes to withdraw from all study participation, the reason(s) will be sought (but do not need to be given). Unless the participant actively states that existing data, and/or future data from medical records may not be used, data will be used in accordance with the original signed ICF.

Participants who were consented by a representative and who are found to have regained capacity during the trial will be given a PIS outlining what their enrolment into the trial has entailed and, if they wish to continue in the trial, will be asked to complete an ICF to be stored in the participant's record and site file. If the participant has been discharged from hospital at the point capacity is regained, telephone or online re-consent is acceptable. If they do not consent to continuing in the study, they will be withdrawn. In this scenario, they will be asked to consent to use of their data. If this is not given, all of their data will be deleted.

A summary of who can give consent for the trial is shown in table below.

| Summary hierarchy of informed consent for an incapacitated adult | | |
|--|---|--|
| England, Wales and Northern Ireland | Scotland | |
| Personal legal representative / consultee | Personal legal representative. | |
| A person not connected with the conduct of the trial who is (a) suitable to act as the legal representative by virtue of their relationship with the adult, and (b) available and willing to do so. Professional legal representative. | 1A. Any guardian or welfare attorney who has power to consent the adult's participation in research. | |
| | 1B. If there is no such person, the adult's nearest relative as defined in section 87(1) of the Adults with Incapacity (Scotland) Act 2000. | |
| | Professional legal representative. | |

Table 3: Summary hierarchy of informed consent for an incapacitated adult

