9 PHARMACOVIGILANCE

9.1 Definitions

| | Term Definition |
|--|-----------------|
|--|-----------------|

| Adverse Event (AE) | Any untoward medical occurrence in a participant to whom a medicinal product has been administered, including occurrences which are not necessarily caused by or related to that product. |
|--|--|
| Adverse Reaction (AR) | An untoward and unintended response in a participant to an investigational medicinal product which is related to any dose administered to that participant. |
| | The phrase "response to an investigational medicinal product" means that a causal relationship between a trial medication and an AE is at least a reasonable possibility, i.e. the relationship cannot be ruled out. |
| | All cases judged by either the reporting medically qualified professional or the Sponsor as having a reasonable suspected causal relationship to the trial medication qualify as adverse reactions. It is important to note that this is entirely separate to the known side effects listed in the SmPC. It is specifically a temporal relationship between taking the drug, the half-life, and the time of the event or any valid alternative aetiology that would explain the event. |
| Serious Adverse Event (SAE) | A serious adverse event is any untoward medical occurrence that: |
| Note: SAEs are further defined in section 9.2 in line with risk adaptation for this trial | Results in death Is life-threatening Requires inpatient hospitalisation or prolongation of existing |
| | hospitalisation Results in persistent or significant disability/incapacity Consists of a congenital anomaly or birth defect |
| | Other 'important medical events' may also be considered serious if they jeopardise the participant or require an intervention to prevent one of the above consequences, e.g. emergency interventions within A&E departments that do not result in hospitalisation such as administration of glucagon/glucose in participants with hypoglycaemia. |
| | NB: The term "life-threatening" in the definition of "serious" refers to an event in which the participant was at risk of death at the time of the event; it does not refer to an event which hypothetically might have caused death if it were more severe. |
| Serious Adverse Reaction (SAR) | An adverse event that is both serious and, in the opinion of the reporting Investigator, believed with reasonable probability to be due to one of the trial treatments, based on the information provided. |

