10.7 Participant population

Primary efficacy analyses will be undertaken according to the intention to treat principle. Complier average causal effects analysis will be used to estimate the average treatment effect in those treated.

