10.8 Potential risk of missing or spurious data

The main analyses will use complete case data. Factors associated with availability of follow-up data will be assessed using logistic regression. Sensitivity analyses will include multiple imputation of missing outcome data.

Data will be gathered from the medical record by investigators. Missing data will be identified and queried by data management on a regular basis.

Participants and consented caregivers will provide their contact details at enrolment for the Day 90 follow-up. Outcome assessors will attempt to contact participants and caregivers to arrange a suitable time to complete the questionnaires. Where possible, data not obtained via telephone follow-up will be gathered from the participants' medical records.

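### Section 7.9.2 lets unblinded investigators end study participation for SARs, protocol violations or administrative reasons, which can put arm-related gaps in a complete-case primary analysis

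*Protocol*

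**What the plan says.** Two rules govern stopping.

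- **Treatment (7.9.1).** Local teams may stop clarithromycin for a SAR, and a list of further events requires it. The section closes: "Discontinuation of treatment by local clinical teams does not require withdrawal of the participant from the study and follow-up can be continued".
- **Study (7.9.2).** The chief investigator, co-chief investigator and site investigators may "withdraw patients from the study if deemed in the best interests of the participant or in the event of SARs, protocol violations", and also for administrative or other reasons. Afterwards: "Participants who withdraw from the study can consent to their vital status being checked and follow-up via medical records if they wish". No central mRS interview is provided for after withdrawal from the study.

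On analysis, section 10.7 states: "Primary efficacy analyses will be undertaken according to the intention to treat principle", and 10.3.2 says the same of the primary outcome. Section 10.8 states: "The main analyses will use complete case data". Multiple imputation is a sensitivity analysis there, and medical records are a back-up source.

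Section 9.1 defines an adverse reaction as: "An untoward and unintended response in a participant to an investigational medicinal product which is related to any dose administered to that participant". Section 8.1 names clarithromycin as the IMP, and 8.11 says there are no NIMPs. Section 7.4 says that care providers are not blinded.

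**The concern.** Withdrawal from the study is a post-randomisation decision made by people who know the allocation. One of its listed grounds, a SAR, can arise only where the IMP is given. A survivor withdrawn on that ground with no day-90 mRS drops out of a complete-case analysis. The intention-to-treat label does not bring that outcome back, and no SAP can recover data that sites were allowed not to collect.

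The SAR ground does no work that 7.9.1 does not already do. Stopping the drug is covered there, with follow-up continued. At study level all it adds is the possibility of losing the primary outcome. If those lost have outcomes unlike the rest of their arm, the estimated common odds ratio is biased.

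**Working it through.** **Step 1. Does the clause reach the primary analysis?**

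- 7.9.2 ends study participation; 7.9.1 ends treatment only.
- An adverse reaction requires a dose of the IMP (9.1). Clarithromycin is the only IMP (8.1) and goes only to the intervention arm (7.3). The SAR ground is therefore confined to that arm. Protocol violations and administrative reasons can occur in either arm.
- The main analysis uses complete cases (10.8), so a withdrawn participant without an mRS does not contribute.

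**Step 2. Reproduce the plan's sample size (10.1).** Inputs: control mRS distribution 2:8:8:5:20:20:37, common OR 0.7, two-sided 5%, 90% power. The proportional-odds formula is

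N = 12 (z₀.₉₇₅ + z₀.₉₀)² / {[ln OR]² (1 − Σ p̄ᵢ³)},

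where p̄ is the mean of the two arms' distributions. Here Σ p̄ᵢ³ = 0.0546, so N = 12 (1.960 + 1.282)² / {0.3567² × 0.9454} ≈ 1048, or 524 per arm. Attrition: 524 / 0.9 = 582.2, rounded up to 583 per arm, 1166 in total. Both match the protocol.

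Power is not the issue. An extra 5% loss in the clarithromycin arm, beyond the planned 10%, takes power from 0.900 to 0.893.

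**Step 3. Illustrate the bias under no true effect.** The protocol gives no expected number of SARs or investigator withdrawals. The share lost, w, is therefore an assumption: 2%, 3% or 5% of 524, that is 10.5, 15.7 or 26.2 people.

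Both arms start from the control distribution p. If those lost have outcome distribution d, the observed clarithromycin distribution is

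q = (p − w d) / (1 − w).

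The common OR of q against p is fitted by maximum likelihood. With N = 1048 (1 − w/2) and V = (N/12)(1 − Σ p̄ᵢ³), the shift in the test statistic is s = ln(OR) √V. The chance of a one-sided result at p < 0.025 (10.6) is Φ(−1.96 − s). The calculation treats the final test as a single look, without covariate adjustment.

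Worked case, w = 5%, all lost would have died: the observed share at mRS 6 is (0.37 − 0.05)/0.95 = 0.337. The OR is 0.899, with ln OR = −0.106. N = 1021.8 and V = (1021.8/12)(1 − 0.0627) = 79.8, so √V = 8.93. Then s = −0.948 and Φ(−1.012) = 0.156.

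| Outcomes of those lost | 2% lost: OR (error) | 3% lost: OR (error) | 5% lost: OR (error) |
|---|---|---|---|
| All would have died, deaths unrecorded | 0.960 (5.6%) | 0.939 (8.1%) | 0.899 (15.6%) |
| Half mRS 5, half mRS 6 | 0.978 (4.0%) | 0.966 (4.9%) | 0.943 (7.5%) |
| Typical of the arm | 1.000 (2.5%) | 1.000 (2.5%) | 1.000 (2.5%) |
| Deaths kept, only survivors' mRS lost | 1.025 (1.5%) | 1.038 (1.1%) | 1.065 (0.6%) |

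The last row is bias against clarithromycin. The direction turns on whether deaths are retained.

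**Step 4. Would deaths be retained?** The sections do not agree. The last paragraph of 7.9.2 makes vital status and record follow-up something that withdrawing participants can opt into. Section 7.2.1 sets the opposite default: existing data and future record data are used unless the participant actively objects. Section 7.6 has local staff collect mortality from the record, 8.9 says relevant data should continue to be collected while consent stands, and 9.10 requires every death in the eCRF. The sentence in 7.9.2 does not say what applies when the investigator, rather than the participant, withdraws.

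**The case against.** The strongest reply is that 7.9.2 grants a permission and the surrounding rules favour keeping people in. Section 7.9.1 says "Discontinuation of treatment by local clinical teams does not require withdrawal of the participant from the study", 8.9 continues data collection after treatment stops, and 8.12 keeps usual-care participants who come to need a macrolide. No section removes withdrawn participants from the analysis set, and 10.8 offers record retrieval, modelling of follow-up availability and multiple imputation. All of this stands. It limits the likely number of losses and means that the clause does not flatly contradict intention to treat. It does not explain why SARs and violations should be grounds for ending follow-up at all. Multiple imputation, as a sensitivity analysis, does not change the main result.

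A reader might infer more than the protocol supports:

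- **That the clause removes mainly clarithromycin patients.** One-sidedness is shown only for SARs.
- **That it inflates type I error in favour of clarithromycin.** The 5.6% to 15.6% figures need every lost participant to be an unrecorded death. Sections 7.2.1, 7.6 and 9.10 make deaths the outcome most likely to be kept, and the bias then reverses.
- **That the re-consent rule in 7.2.1 ("If this is not given, all of their data will be deleted") is part of the same fault.** That rule acts in both arms, on people who regain capacity and refuse both continuation and use of their data. It does not support a bias towards clarithromycin, and changing it would need ethics committee agreement.

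**Conclusion.** The point holds as a defect in a stated rule. Section 7.9.2 permits discretionary, unblinded, post-randomisation withdrawal from the study. One of its grounds exists only in the clarithromycin arm, and the main analysis drops participants without an mRS. The primary comparison can therefore depart from intention to treat.

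The protocol fixes neither the size nor the direction of any bias. Across the assumed 2% to 5% loss, one-sided type I error runs from 0.6% to 15.6% against a nominal 2.5%, depending wholly on who is lost and whether their deaths are recorded. The loss shares and outcome mixes are assumptions; the mRS distribution, 524 per arm and the 0.025 threshold are the protocol's. No sample-size figure changes. This should be corrected, preferably before recruitment because uncollected outcomes cannot be recovered, but it does not show that the trial's result will be biased.

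**What to change.** Reword 7.9.2 so that SARs, protocol violations and administrative reasons may end study treatment, with a cross-reference to 7.9.1, but do not end outcome collection. State that the day-90 vital-status check and the blinded mRS remain due for every randomised participant unless the participant or their representative withdraws from follow-up.

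Reconcile the opt-in sentence in 7.9.2 with the opt-out default in 7.2.1 and with the continued follow-up in 7.9.1 and 8.9. Say which rule applies when the investigator initiates the withdrawal.

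Leave the best-interests ground and the re-consent deletion rule in 7.2.1 out of this change. The cost is protocol wording and matching site guidance. The change alters no criterion for stopping clarithromycin, no participant's right to withdraw and no sample-size figure.
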